|-------------------|---|
| T | Tesla |
| TBS | Theta Burst Stimulation |
| TEAE | Treatment Emergent Adverse Event |
| | Treatment Expectations and Experience Questionnaires |
| TEEQ-A and TEEQ-P | Adolescent and Parent Versions |
| TMS | Transcranial Magnetic Stimulation |
| TORDIA | Treatment of Resistant Depression in Adolescents |
| UADE | Unanticipated Adverse Device Effect |
| | Unanticipated Problems Involving Risk to Participants or Others |
| UPIRTSO | Others |
| YMRS | Young Mania Rating Scale |

Study Summary

| | |
|---------------------------------------|--|
| Title | Glutamatergic and GABAergic Biomarkers in rTMS for Adolescent Depression |
| Running Title | Adolescent Biomarker Guided rTMS |
| IRB Protocol Number | 17-004958 |
| Phase | Pivotal |
| Methodology | Phase I is a double-blind, randomized, biomarker-stratified trial of 1 Hz vs. 10 Hz rTMS. Phase II is for participants who do not respond to Phase I treatment and is a biomarker guided, double-blind trial of continuous vs intermittent theta burst stimulation (TBS). Please note that transcranial magnetic stimulation (TMS) biomarkers will be collected in this protocol during the course of the proposed interventions. Participants in Phase I will also be offered 3 and 7 Tesla Magnetic Resonance Imaging (MRI) and Magnetic Resonance Spectroscopy (MRS) scans at the University of Minnesota Center for Magnetic Resonance Research. |
| Overall Study Duration | 5 years |
| Participant Time Commitment | Phase I – 6 months (1 week screening, 6 weeks of active treatment, 6 month follow up visit) Phase II- 6 months (1 week screening, 2 weeks of active treatment, 6 month follow up visit) |
| Objectives | To perform an effectiveness and target validation trial of 1 Hz vs. 10 Hz rTMS with a randomized, biomarker-stratified design. The target engagement and stratification biomarker is intracortical facilitation (ICF) a measure of glutamatergic tone in the brain. Cortical GABA, glutamate, and glutamine measured with 7 Tesla MRS will be collected in healthy controls at baseline and depressed participants at baseline and after 6 weeks of TMS treatment in phase I. |
| Number of Participants | Phase I- 120 participants Phase II- 50 participants (maximum) MRI – 100 Depressed Subjects (Must be Eligible for Phase I) 30 Healthy Controls |
| Diagnosis and Main Inclusion Criteria | Depressed adolescent (ages 12-18) participants with moderate to severe major depressive disorder (MDD) defined by a score of 40 or greater on the Children’s Depression Rating Scale, Revised (CDRS-R) and an interview with the Mini International Neuropsychiatric Interview (MINI). |
| Study Device | NeuroStar® TMS Therapy System in XPLOR research configuration |

| | |
|--------------------------------|---|
| 
Duration of Exposure
 | 
Phase I - 6 weeks (30 sessions) and 3 week taper (3 sessions for one week, then 2 sessions for the next week, then 1 session for the last week of the taper). Based on randomization participants will either receive sessions of 1 Hz rTMS at 120 % motor threshold (MT) with 2400 continuous pulses or 10 Hz rTMS at 120 % MT with 4 seconds on and 36 seconds off for 2400 pulses. Both 1 Hz and 10 Hz rTMS sessions will be delivered to the left dorsolateral prefrontal cortex (LDLPFC).
 
Phase II- 2 weeks (10 sessions) of continuous theta burst (cTBS) or intermittent theta burst (iTBS) based on biomarker (ICF) status. Note that TBS sessions involve the delivery of 3 pulses of 50 Hz stimulation given every 200 milliseconds (ms) or 5 Hz. Participants assigned to cTBS will receive 10 daily sessions (5 sessions per week for two weeks) with 120 second trains of uninterrupted TBS for 1800 pulses at 80% MT. Participants assigned to iTBS will receive 10 daily sessions (5 sessions per week for two weeks) with 2 second trains every 10 seconds for a total of 570 seconds for 1800 pulses. Both cTBS and iTBS sessions will be delivered to the LDLPFC.
 
NeuroStar TMS is not an implant. Stimulation is delivered during the daily sessions in the neurostimulation suite.
 |
| 
Reference therapy
 | 
Not Applicable
 |
| 
Statistical Methodology
 | 
For the primary aim, a linear mixed model analysis of repeated measures will be used to evaluate the repetitive transcranial magnetic stimulation (rTMS) by biomarker status interaction effect on depression severity (CDRS-R score) over 6 weeks of rTMS.
 
For the secondary aim, a within-participant linear mixed model analysis of repeated measures will be used to examine the change in ICF over 6 weeks of rTMS.
 
For the exploratory aims, a within-subjects linear mixed model analysis of repeated measures will be used to examine the change in cortical MRS measures of GABA, glutamate, and glutamine over 6 weeks of rTMS treatment in depressed adolescents. A multiple mediation/moderation path analytic model will be used to estimate the direct effect as well as the total and specific indirect effects of rTMS treatment on depression severity (at the 6-week endpoint) through each potential baseline moderator (anhedonia and adversity).
 |

1 Introduction

This document is a protocol for a human research study. This study will be carried out in accordance with the procedures described in this protocol, applicable United States government regulations and Mayo Clinic policies and procedures.

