2.1 Primary Objective

Aim 1 examines the relative efficacy of 6 weeks low frequency (1 Hz) or high frequency (10 Hz) left prefrontal rTMS according to a baseline ICF (**ICF-15 % MEP amp**) measure of glutamatergic tone in depressed adolescents. We will employ a biomarker stratified design. Depressed adolescents will be stratified by baseline ICF low (≤ 1.5) or ICF high (>1.5) groups prior to randomization.

- We expect that 6 weeks of 1 Hz rTMS will have greater efficacy (assessed by improvement in CDRS-R) in depressed adolescents with high baseline ICF compared to adolescents with low baseline ICF.
- We expect that 6 weeks of 10 Hz rTMS will have greater efficacy (assessed by improvement in CDRS-R) in depressed adolescents with low baseline ICF compared to adolescents with high baseline ICF.
- 6 weeks of 1 Hz rTMS will have greater efficacy (assessed by improvement in CDRS-R) than 6 weeks of 10 Hz rTMS in depressed adolescents with high baseline ICF.
- 6 weeks of 10 Hz rTMS will have greater efficacy (assessed by improvement in CDRS-R) than 6 weeks of 1 Hz rTMS in adolescents with low baseline ICF.

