5.2 Method for Assigning Participants to Treatment Groups

Each participant will be assigned a unique identification upon signing the informed consent and assent form. This number will consist of an assigned 3-digit identifier. Participants will be identified by their assigned number and initials on the CRFs and source documents. The PI/Study Sponsor will maintain a master list linking Participant names and the identifying information indicated above

A Phase I randomization schedule will be generated by [name] (Study biostatistician). Participants will not be randomized until all entry (inclusion and exclusion) criteria have been met and all pre-study procedures have been satisfactorily completed. After stratification based on ICF biomarker status, eligible participants will be randomly assigned to receive one of the two treatment regimens (1 Hz or 10 Hz rTMS), and the next available randomization number for the participant's stratum will be recorded in the screening log and on the participant's CRF. Randomization numbers may not be reassigned. A permuted-block procedure will be used to randomly assign the treatment conditions, with a fixed block size for each stratum. Phase II is a trial of cTBS or iTBS for Phase I participants who did not have an adequate clinical response in Phase I. Participants will be assigned to 2 weeks of cTBS if their intracortical facilitation measure is >1.5 (building on the current speculation that cTBS would be expected to decrease cortical excitability and ICF measures). Participants will be assigned to 2 weeks of iTBS if their ICF (baseline assessment for TBS extension trial) is ≤ 1.5 .

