7.1 Sample Size Determination

Sample Size Estimation and Power Analysis for the Primary Aim of the Study

Using a putative estimate of effect size ($d \sim 0.61$) as it relates to the Primary Aim, an *a priori* sample size estimation and power analysis was performed for the repeated measures design in the proposed study. The results suggest that a sample size of 25 participants per group ($N=120$) achieves 80% power, at a 0.05 alpha level (two-tailed), to detect standardized group mean differences (Cohen's d) as small as 0.61 in a 2-treatment by 2-biomarker status between-Participants group design with 6 (within-Participants) repeated measurements of the primary outcome (depression severity) having a compound symmetry covariance structure, when the assumed within-Participant correlation between observations (depression severity) on the same Participant is ≤ 0.50 (0.50 was based on guidance from our preliminary rTMS work). We anticipate some dropouts (~20% based on treatment discontinuation results from our previous rTMS studies). Thus, ~120 participants will be enrolled to allow for this expected rate of attrition with the intent of capturing a range of evaluable data for 100 participants. The Power Analysis and Sample Size (PASS) 2016 software, version 14.0.7, was used to carry out the sample size and power analysis.⁸⁹

We recognize that to definitively evaluate the relationship between rTMS Treatment (low frequency 1 Hz rTMS vs. high frequency 10 Hz rTMS) by biomarker status (high baseline ICF vs. low baseline ICF) on depression severity—since this relationship has not been previously studied, we have no previous findings to guide effect size selection for the present effort, and the current study would be the first of its kind to examine this effect in depressed youth—we will possibly need a larger sample size than the 100 participants put forth in this proposal. The selection of 100 participants was, in part, resource-driven. The sample size is designed, in part, to detect a moderate effect and to establish a *proof of concept* so as to expand to a subsequent, larger-scale multi-center study. Nevertheless, the current proposal will permit an evaluation of whether receiving low frequency (1 Hz) rTMS vs. high frequency (10 Hz) rTMS treatment according to patients' baseline biomarker status (ICF) shows initial evidence of a relationship with improvement in depression severity in a depressed adolescent population.

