MIXED procedures (mixed model approach) in SAS software will make use of all available data from all participants from the efficacy analysis set, and provide a robust mechanism for handling data that are assumed missing at random (see sensitivity analysis section below for MNAR).

Secondary Aim

Data Analysis Plan for Secondary Aim 2 (Hypotheses 2a–2d)

Secondary Continuous Outcome: Intracortical Facilitation (ICF)

Intracortical Facilitation over the 6-week study period will be the secondary continuous outcome measure. A within-Participants linear mixed model analysis of repeated measures will be used to examine the change in ICF over 6 weeks of rTMS treatment in depressed adolescents. We will consider the inclusion of pubertal state and treatment resistance (as defined by ATHF score) during the study period as a covariate in the mixed model. A mixed model analysis will be conducted on ICF for those who receive 6 weeks of low frequency (1 Hz) rTMS treatment (Hypothesis 2a) and, in a separate model, for those who receive 6 weeks of high frequency (10 Hz) rTMS treatment (Hypothesis 2c). Restricted maximum likelihood estimation, Type 3 tests of fixed effects, and generalized least squares (LS) will be used, with the Kenward-Roger correction applied to the appropriate and best fitting covariance structure. The sandwich (robust covariance matrix) estimator will also be considered. LS mean contrasts (between ICF measurement time periods) from the mixed model will also be examined. A separate linear mixed model analysis similar to that described above will also be implemented over 6 weeks of acute rTMS treatment and throughout the 6-month follow-up period. A nonlinear mixed model will be considered (e.g., exponential decay/growth model) to estimate ICF over the 6 weeks of rTMS treatment (if the pattern of ICF values suggests that a nonlinear model is deemed necessary).

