A linear mixed model repeated measures analysis similar to that described above will also be used to examine the relationship between measures of ICF (as the response variable) and depressive symptoms (CDRS-R total as a time-varying covariate) over the 6 weeks of rTMS treatment. We will consider the inclusion of pubertal state and treatment resistance (as defined by ATHF) during the study period as a covariate in the mixed model. The parameter estimates (regression coefficients) will be interpreted from the solution for fixed effects in the mixed model analysis for those who receive 6 weeks of low frequency (1 Hz) rTMS treatment (Hypothesis 2b) and for those who receive 6 weeks of high frequency (10 Hz) rTMS treatment (Hypothesis 2d). A separate linear mixed model analysis similar to that described above will also be implemented over 6 weeks of acute rTMS treatment and throughout the 6-month follow-up period. A nonlinear mixed model will be considered to estimate ICF over the 6 weeks of rTMS treatment from CDRS-R total (if the pattern of ICF and CDRS-R total suggests that a nonlinear model is deemed necessary).

Data Analysis Plan for Exploratory Aim 3 (MRI/MRS)

A within-participants linear mixed model analysis of repeated measures will be used to examine baseline differences between depressed adolescents and healthy control adolescents (Hypotheses 1 and 2); and the change in cortical MRS measures of GABA and Gln/Glu over 6 weeks of rTMS treatment in depressed adolescents. Separate mixed models will be conducted on cortical GABA and Gln/Glu for those who receive 6 weeks of low frequency (1 Hz) rTMS treatment

(Hypotheses 3 and 4) and for those who receive 6 weeks of high frequency (10 Hz) rTMS treatment (Hypotheses 5 and 6). A nonlinear mixed model will be considered (if the pattern of GABA and Gln/Glu values suggests that a nonlinear model is deemed necessary).

Data Analysis Plan for Exploratory Aim4

Moderator Effects of Anhedonia and Adversity on Treatment Outcome of Depression Severity

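### The Aim 2 models leave out the ICF stratum, so if Aim 1 is true the single ICF-on-CDRS-R coefficient per arm is pulled towards zero

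*Combined protocol and SAP*

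**What the plan says.** Randomisation uses the biomarker (section 5.2): "After stratification based on ICF biomarker status, eligible participants will be randomly assigned to receive one of the two treatment regimens". The cut-off is 1.5. Section 2.1 expects that "6 weeks of 1 Hz rTMS will have greater efficacy (assessed by improvement in CDRS-R) in depressed adolescents with high baseline ICF" than in those with low baseline ICF, and the reverse for 10 Hz. The Aim 1 model in section 7.2 accordingly has biomarker status and its interaction with treatment.

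For Aim 2, the Study Summary says that "a within-participant linear mixed model analysis of repeated measures will be used to examine the change in ICF over 6 weeks of rTMS". Section 7.2 states: "A mixed model analysis will be conducted on ICF for those who receive 6 weeks of low frequency (1 Hz) rTMS treatment (Hypothesis 2a", with a separate model for the 10 Hz arm. For hypotheses 2b and 2d it examines "the relationship between measures of ICF (as the response variable) and depressive symptoms (CDRS-R total as a time-varying covariate" and interprets the coefficient for each arm. Pubertal state and ATHF score are the only covariates under consideration. No stratum term, stratum interaction or stratum-specific estimate is mentioned.

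The Aim 2 hypotheses in section 2.2 are worded for whole arms: ICF falls on 1 Hz and rises on 10 Hz, and the symptom relation is stated per arm.

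**The concern.** In the 1 Hz arm, hypothesis 2b expects ICF and CDRS-R to fall together within a person, so the slope of ICF on CDRS-R is positive. If Aim 1 holds, the high-ICF participants in that arm improve more. During treatment they have higher ICF and lower CDRS-R than the low-ICF participants, which is a negative association between people. A mixed model with CDRS-R as an undivided time-varying covariate blends the two sources. Without the stratum, the between-person part pulls the coefficient towards zero.

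The 10 Hz arm is the mirror image, if section 2.2 is read as ICF rising while CDRS-R falls: the low-ICF participants improve more, giving a positive between-person association against a negative predicted slope.

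So success on Aim 1 would weaken the Aim 2 evidence meant to explain it. If the slope also differs between strata, one coefficient per arm averages over that difference.

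**Working it through.** **The plan's own figure.** Section 7.1 gives power for the primary aim only: "a sample size of 25 participants per group ($N=120$) achieves 80% power", "at a 0.05 alpha level (two-tailed", for "standardized group mean differences (Cohen's d) as small as 0.61", with 6 measurements and correlation 0.50. The SD of a participant mean is sqrt((1 + 5 x 0.5)/6) = 0.764. For 25 against 25, the noncentrality is (0.61/0.764) x sqrt(25/2) = 2.82, and power is Phi(2.82 - 1.96) = 81%. The 80% is reproduced, for one cell against another. No power, ICF SD or ICF effect is given for Aim 2, so what follows rests on assumptions.

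**Attenuation with equal slopes.** Simulated 1 Hz arm, 2,000 runs per scenario:

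- 25 participants per stratum (section 5.3 expects an even split) and 7 visits (baseline and weeks 1-6, Table 3).
- Assumed CDRS-R: baseline mean 60, SD 8; mean fall 25 points in high ICF and 10 in low ICF, SD 8; visit-level SD 4.
- Assumed ICF: stratum means 0.6 or 1.0 apart, between-person SD 0.2, residual SD 0.35.
- True within-person slope in the high stratum: 0.006 ICF units per CDRS-R point.
- Random-intercept model of ICF on CDRS-R. Power is the share of runs with z > 1.96 in the predicted direction.

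| Slope in low stratum | No stratum term: slope (power) | With stratum main effect: slope (power) |
|---|---|---|
| Same, 0.006 | 0.0031-0.0036 (30-35%) | 0.0046-0.0047 (63-64%) |
| Half | 0.0023-0.0028 (19-24%) | 0.0039-0.0040 (49-50%) |
| Zero | 0.0016-0.0022 (12-16%) | 0.0033-0.0034 (37-39%) |
| Opposite | 0.0003-0.0004 (4%) | 0.0020-0.0021 (16-18%) |

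With equal slopes, the model without the stratum recovers 0.0031/0.006 = 52% to 0.0036/0.006 = 60% of the truth. With the stratum it recovers 77-78%. The high stratum analysed alone gives about 0.005, with power 50-54%.

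Over a wider set of assumed ICF SDs, again with equal slopes, the slope without the stratum was 0.0013-0.0050 (22-83% of 0.006; power 8-80%). With the stratum main effect it was 0.0041-0.0054 (68-90%; power 25-89%). The stratum term was better in every setting.

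These models have no visit effect. A check with visit as a factor gave stronger attenuation and the same ordering.

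**Averaging over unequal effects.** This part sets the between-person problem aside and treats each effect as purely within-person. Let r be the effect in the other stratum divided by that in the matched stratum. Take an effect with 80% power in 25 matched participants: noncentrality 2.80, or 2.80/sqrt(25) = 0.56 per participant. Pooling 50 gives 0.56 x sqrt(50) x (1 + r)/2 = 3.96 x (1 + r)/2.

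| r | Noncentrality | Pooled power |
|---|---|---|
| 1 | 3.96 | 98% |
| 0.5 | 2.97 | 84% |
| 0.25 | 2.48 | 70% |
| 0 | 1.98 | 51% |
| -0.5 | 0.99 | 17% |
| -1 | 0 | 2.5% |

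Pooling equals the matched stratum alone when (1 + r)/2 = 1/sqrt(2), so r = 0.41. For matched shares of 30% to 60%, break-even lies between 0.35 and 0.44.

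**What stratum contrasts can show.** Within one arm, 25 against 25 has noncentrality 0.56 x (1 - r) x sqrt(25/2) = 1.98 x (1 - r): 51% power at r = 0 and 17% at r = 0.5.

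**The case against.** The Aim 2 hypotheses are arm-level, and the per-arm ICF change models test them. That stands for 2a and 2c. A reader might infer that target engagement cannot be shown where it is predicted. The documents do not support that, because section 2.2 predicts it for each whole arm.

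A reader might also infer that the two strata cancel. That needs a reversed slope, or no slope and no improvement, in the other stratum. Section 2.1 says only that efficacy is greater in one stratum.

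Nor does Aim 1 force a weaker slope in the mismatched stratum. ICF is the response, so an equal ICF change over a smaller CDRS-R change gives a steeper slope there. With a common slope and a purely within-person coefficient, pooled power is 98%. This also stands, but section 7.2 does not plan a purely within-person coefficient, and the equal-slope loss comes from the between-person part.

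One might expect the stratum to sharpen the arm-level ICF change too. With a 25/25 split and complete data, the estimated mean change is the same number with or without stratum x time.

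Finally, this is a secondary aim with no power claim, in a study that section 7.1 calls a proof of concept. That limits the weight of the point, but the remedy is nearly free.

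**Conclusion.** The omission is clear: section 7.2 uses the ICF stratum for Aim 1 and not for Aim 2. The consequence is attenuation of the 2b/2d coefficient under Aim 1's own premise, to roughly 20-80% of the true slope across the assumed settings, even with equal slopes. It is larger if the slope is weaker in the other stratum. Apart from this between-person effect, pooling beats the matched stratum alone unless the other stratum's effect is below about 41% of the matched one.

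The sizes depend on assumed ICF SDs, stratum gap, slope and CDRS-R falls, on an even split, and on a random-intercept model with undivided CDRS-R. The direction follows from Aim 1 being true. Hypotheses 2a and 2c remain testable as planned, and neither cancellation nor an inability to show engagement is established.

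**What to change.** In section 7.2, before analysis:

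1. In the 2b/2d models, add baseline ICF stratum as a fixed effect, with stratum x CDRS-R as a supporting term. Report the slope averaged over strata and within each stratum. The stratum main effect does not remove all the attenuation; splitting CDRS-R into person mean and deviation would address the rest.
2. For ICF change, keep the arm-level result and add one joint model of both arms with treatment x stratum x time. Read stratum-specific change only as the 1 Hz minus 10 Hz difference within a stratum. The strata are cut on the first ICF value of the outcome series, so regression to the mean lowers ICF in the high stratum and raises it in the low stratum in both arms. A single-arm change within a stratum would therefore mimic engagement in each matched cell. The separate per-arm models now planned cannot give this contrast.

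The cost is analysis-plan wording, a few model terms and one joint model; the stratum is already recorded for everyone randomised. The downside is imprecision: with about 25 per cell, stratum-specific results should be given as estimates with confidence intervals, not as powered tests.

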1.1 Background

Adolescent depression is a substantial global public health problem which contributes to academic failure, occupational impairment, deficits in social function, substance use disorders, teen pregnancy, and completed suicides.¹⁻³ Existing treatment approaches such as psychotherapy, pharmacotherapy, or combinations often have suboptimal results and uncertain safety profiles.³⁻⁶ For example, ongoing controversies regarding the effectiveness and safety of selective serotonin reuptake inhibitors underscore the concern that current treatment modalities do not target relevant, pathophysiology in a neurodevelopmentally informed manner.⁵ This is a lost opportunity as intervention early in life could prevent years of disability and suffering on an individual level and a substantial societal economic burden. Unfortunately, interventions for adolescent depressive disorders are often simply adapted from existing adult treatments and studied in heterogeneous groups of adolescents.⁷ Dimensional and experimental medicine approaches offer the opportunity to optimize existing treatment options and catalyze innovation for adolescent depression.^{8,9} For example, anhedonia and historical adversity are key elements of the negative valence systems domain and markers of treatment resistance.¹⁰⁻¹² A refined understanding of anhedonia and adversity would provide the opportunity to develop targeted treatment approaches.

Imbalances in GABAergic and glutamatergic tone play a key role in depression,^{13,14} pathophysiologic stress responses,¹⁵ and emotional numbing or anhedonia found in behavioral manifestations of the negative valence system.¹⁶ These GABAergic and glutamatergic imbalances have differential causes, effects, and behavioral manifestations in adolescents as compared to adults.¹⁷⁻¹⁹ For example, recent preclinical work has demonstrated that repeated stress in adolescent rats inhibits GABAergic projections to the amygdala thereby impairing regulatory neurocircuitry.²⁰ In adult rats, chronic stress facilitates glutamatergic excitatory neurotransmission with ensuing effects on the lateral nucleus of the amygdala, hippocampus, and frontal cortex.²¹⁻²³ Developmental differences in frontolimbic GABAergic and glutamatergic tone may underlie variances in adolescent depressive symptom presentations and treatment responsiveness.^{20,24,25} A deeper understanding of frontolimbic GABAergic and glutamatergic tone in adolescent depression would assist with precision medicine approaches and intervention development. Certain types of transcranial magnetic stimulation (TMS) provide noninvasive measures of cortical GABAergic and glutamatergic tone.²⁶⁻²⁸ There are different types of TMS. Repetitive TMS (rTMS) delivers multiple pulses per session over many days or weeks for therapeutic purposes. The effects of rTMS can also be studied as a probe of brain function. Theta burst stimulation (TBS) is a form of rTMS that is thought to have more rapid effects on synaptic plasticity and clinical symptoms than standard rTMS. Single and paired-pulse TMS paradigms are used to study the physiology of the brain. Neurophysiological measures collected with transcranial magnetic stimulation (TMS) such as intracortical facilitation (ICF), short-interval intracortical inhibition (SICI), long-interval intracortical inhibition (LICI), and the

cortical silent period (CSP) are noninvasive measures of cortical GABAergic and glutamatergic tone.²⁸⁻³¹

Neurostimulation technologies such as rTMS have great potential as enduring, brain-based interventions for depression in adolescents.^{32,33} Treatment with rTMS addresses pathologic imbalances in cortical GABAergic inhibitory and excitatory glutamatergic frontolimbic neurocircuitry.³⁴⁻³⁶ At present, adults with broad presentations of depression are typically treated empirically with high frequency (10 Hz) rTMS applied to the LDLPFC as this dosing approach has been widely studied.^{37,38} However, prior literature suggests that low frequency (1 Hz) rTMS applied to the right dorsolateral prefrontal cortex (RDLPFC) may be equally effective with superior tolerability.³⁹⁻⁴² Left-sided, 1 Hz rTMS applied to the LDLPFC may have similar antidepressant and neurophysiologic effects as RDLPFC 1 Hz rTMS. For example, early studies with positron emission tomography⁴³ and near infrared spectroscopy⁴⁴ suggest that prefrontal 1 Hz rTMS has a global, bilateral effect on brain activity. Questions of laterality in therapeutic 1 Hz rTMS have been inadequately studied and prior research often utilized right-sided 1 Hz based on dogma more than science.⁴⁵⁻⁴⁷ Other work posits that patients with depression may have variable responses to these two dosing strategies (1 Hz vs. 10 Hz) necessitating a more sophisticated neurobiological understanding and precision medicine approaches.^{34,48} Although rTMS has demonstrated promise for adolescent depression, the mechanisms of 1 Hz vs. 10 Hz rTMS dosing have not been adequately studied in adolescent depression, creating a substantial knowledge gap.³³ Research in this area is critical as the neurobiologic effects of 1 Hz and 10 Hz rTMS in adolescent depression likely diverge from adult depression.⁴⁹⁻⁵¹ The study of 1 Hz rTMS in adolescents is particularly critical as it would have advantages in terms of safety and tolerability for widespread dissemination. A basic, neurodevelopmentally informed understanding of standard rTMS dosing approaches (1 Hz and 10 Hz) is an ethical and scientific prerequisite for future large, pivotal studies of patterned dosing such as TBS for adolescent depression.^{51,52}

Currently our group is leading a multicenter randomized, sham-controlled trial of rTMS for adolescent depression (A Randomized, Sham-Controlled Trial Evaluation of the Safety and Effectiveness of NeuroStar Transcranial Magnetic Stimulation (TMS) Therapy in Depressed Adolescents). Phase I of the study is a 6 week (30 treatment sessions), randomized, sham-controlled study of 10 Hz rTMS delivered to the left dorsolateral prefrontal cortex (LDLPC). The rTMS is targeted and dosed with the abductor pollicis brevis, “5-cm rule.” Phase II is a 6 week open-label treatment course of 10 Hz rTMS for participants who did not respond to treatment in Phase I. Phase III is a follow-up phase for subjects that had clinical benefit in Phase I or II. The target enrollment for this study is 100 participants. Presently, 99 participants have enrolled and it is anticipated that enrollment will close in late 2017 or early 2018. Hence, the proposed dose finding and target validation study would not be expected to run concurrently with the existing industry trial. While the current industry supported effort will provide important systematic data and practical experience, the study design has inherent limitations. As a result, findings will not substantially advance the mechanistic understanding of rTMS in the context of neurodevelopment.^{2,5} First, the industry supported study design replicates a longstanding flaw of interventional work in children and adolescents (spanning psychotherapy, pharmacology, and novel therapeutics) in which adult protocols and dosing schedules are simply applied to children or adolescents.⁶⁻⁸ Second, the current industry supported clinical trial will not inform target engagement efforts nor advance understanding of the neurobiological underpinnings of

adolescent depression and responsivity to 10 Hz rTMS. Third, there is a paucity of data on low frequency (1 Hz) rTMS in adolescents and in general.⁹⁻¹¹ Systematic data demonstrating benefit of 1 Hz rTMS in adolescent depression or subpopulations would have utility as this dosing might be more tolerable, safe, and optimal for widespread delivery.

Hence for the present protocol we have designed an effectiveness and target validation trial of 1 Hz vs. 10 Hz rTMS. While the inclusion of a sham arm would be ideal, there are substantial pragmatic and financial barriers to completing such a study as a single site while concurrently addressing other critical National Institute of Mental Health (NIMH) priorities. Studies of 1 Hz rTMS and mechanistic studies of rTMS in adolescents would address a substantial knowledge gap and could provide further innovations. Unfortunately, there is a low probability that this will be studied systematically outside of a federally funded grant and even less likely that the neurobiologic mechanisms associated with 1 Hz and 10 Hz rTMS in adolescent depression will be adequately studied.

Developmentally informed, targeted interventions with rTMS for adolescent depression could reap important gains on an individual and population level as cortical, GABAergic and glutamatergic tone continues to change throughout development setting the stage for important future functions.^{17,53} Prior rTMS research focused on depression often has a fatal flaw as heterogeneous groups of patients have been studied with insufficient clinical characterization.^{33,52} Anhedonia⁵⁴ and adversity^{55,56} in depressed adolescents are important dimensional traits to quantify in terms of GABAergic tone, glutamatergic tone, and treatment responsivity to 1 Hz and 10 Hz rTMS. Examining a cohort of depressed adolescents and healthy controls with TMS neurophysiology would deepen our understanding of the role of GABA and glutamate in the negative valence systems domain.^{56,57}

Prior work demonstrates that anhedonia is a marker of treatment resistance, poor outcomes, and suicidality. For example, recent multivariate analyses from the landmark Treatment of Resistant Depression in Adolescents (TORDIA) study identified a dimensional measure of anhedonia as the primary predictor of increased time to remission and decreased depression-free days in a large (n=334) cohort of adolescents with treatment resistant depression.¹¹ Notably patients with historical sexual or physical abuse also had decreased response rates in the TORDIA study.¹⁰ In other recent work, anhedonia severity in depressed adolescents was associated with illness severity, suicidality, duration of illness, and number of depressive episodes.¹² Although incompletely understood, anhedonia and historical adversity appear to have associations with accentuated disruptions in GABAergic⁵⁸ and glutamatergic^{59,60} tone in frontolimbic circuitry. Recent work demonstrated that adolescents with anhedonia have decreased GABA levels in the anterior cingulate cortex¹⁶ while glutamatergic tone in the basal ganglia was associated with clinical measures of anhedonia.⁶¹ Preclinical work also implicates imbalances of GABAergic and glutamatergic tone in treatment resistance.^{23,62} These collective findings suggest that depressed adolescents with anhedonia or historical adversity are a population in great need of effective, brain-based interventions. Dimensional studies of anhedonia and adversity will assist in the development of targeted, neurobiologically informed treatments.^{8,9}

MRS Biomarkers of GABAergic and Glutamatergic Tones in rTMS Studies

Prior work demonstrated that the glutamine to glutamate ratio (Gln/Glu) is a sensitive measure of cortical glutamate-glutamine cycle dysfunction in severe psychiatric disorders. In our prior MRS study, 6 weeks of 10 Hz rTMS modulated cortical glutamatergic tone in depressed adolescents. Baseline, posttreatment, and 6 month follow up MRS 3 T scans examined glutamate concentrations in 8 cm voxels from the left dorsolateral prefrontal and anterior cingulate cortices (Figure1). Spectroscopic data were collected with an optimized, intermediate echo time, point resolved spectroscopy (PRESS) sequence and 2-dimensional J-resolved averaged PRESS sequence. After 6 weeks of rTMS, mean Gln/Glu ratios increased from baseline and at 6 month follow-up in both voxels with both sequences. Mixed model repeated measures analysis revealed a significant negative relationship between depression severity as assessed with the CDRS-R and the Gln/Glu ratio in the dorsolateral prefrontal cortex ($\hat{b} = -0.00127$; 95% CI, -0.00207 to -0.00048 ; raw $P=.003$; false discovery rate $P=.01$). Hence, throughout treatment and follow-up period, decreases in depressive symptom severity had an indirect relationship to increases in the Gln/Glu ratio. This initial work presents many unanswered questions. Resolving GABA, glutamate, and glutamine at 3 T in a single acquisition is challenging to impossible. Special techniques can be used to quantify each of the neurochemicals separately, but that results in three different acquisitions which dramatically increases acquisition time. Our current methodologies do not adequately resolve cortical GABA concentrations and may yield imprecise measures of glutamine concentrations as Cramer-Rao lower bounds (CRLB) criteria are suboptimal. Current work with 7 T MRS demonstrates promise in resolving and quantifying GABA, glutamate, and glutamine in a single acquisition. To our knowledge, 7 T MRS has not been used to study adolescent depression previously.^{63,64}

Ultra-High Field MRS for Biomarker Development in Adolescent Depression

Recent work in adult humans with 7 T MRS and stimulated echo acquisition mode (STEAM) sequence has enhanced the detection and resolution of glutamate, glutamine and GABA (Figure2). In young adults (18 to 22 years of age), glutamate and glutamine could be quantified separately in the early visual cortex with very low CRLB of $2.0\% \pm 0$ and $2.7 \pm 0.3\%$, respectively which is not possible at 3 T. Additionally, GABA was quantified with CRLB of $13.5 \pm 4.6\%$. The spectra were acquired in 5 minutes from $2 \times 2 \times 2$ cm³ volume of interest placed in the early visual cortex with STEAM sequence (TR = 5 s, TE = 8 ms, number of averages = 64). Additionally, quantified glutamate, glutamine and GABA concentrations from spectra acquired at TE of 8 ms removes a possible confound of changing T2. Good quality data can be obtained in the frontal lobe using a prototype coil.^{63,64}

